### 3.4.5. Premature discontinuation

Patients may withdraw the study at any time at their own willing, without giving further details or justification.

The investigator may also exclude a subject from the study based on his/her clinical judgment:

- general or specific changes in the patient's condition which make the patient ineligible for further assessments according to the inclusion/exclusion criteria
- Non-qualification to perform consecutive cycles (e.g., for toxicity)
- Failure to return for follow-up visits

CONFIDENTIAL

Confidential	MyRisk	Date: 05 February 2024
	Protocol	
	PROTOCOL NUMBER: IBA1160	Version: 5.1

**Number of patients:** 410

**Study enrollment time:** 12 – 18 months

**Total number of visits per patient:** 5

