### 3.5. Study Endpoints

Definition of the assessment of time-related study efficacy endpoints:

Time-related efficacy study endpoints assessment will start at time 0 defined as the start time of the chemotherapy administration on Day 1 of each of the three cycles.

CINV indicators, such as nausea and vomiting, their intensity and frequency and Quality of Life will be evaluated during the acute phase of emesis, from 0 to 24 hours from the start of chemotherapy, in the delayed phase of emesis, from 24 to 120 hours from the start of chemotherapy, and overall during each day (i.e., day 1, 2, 3, 4 and 5) from the start of chemotherapy.

The primary endpoint will be the proportion of complete responses (no emetic episode and no rescue medication), during the overall phase (0-120h), after the start of the MEC administration over three cycles of chemotherapy.

Clinical secondary endpoints will be evaluated during each cycle:

- Complete response during the acute (0-24h), delayed phase (>24-120h), overall (0-120h) and daily in each cycle;
- No emetic episode during the acute, delayed and overall phase and daily in each cycle;
- Number of vomiting episodes during the acute, delayed and overall phase and daily in each cycle;
- No rescue medication during the acute, delayed and overall phase and daily in each cycle;
- No significant nausea (maximum MAT scale = 2) during the acute, delayed and overall phase and daily in each cycle;
- No nausea (MAT scale = 0) during the acute, delayed and overall phase and daily in each cycle;
- Complete protection (no emetic episode, no rescue medication and no significant nausea) during the acute, delayed and overall phase and daily in each cycle
- Nausea and Vomiting-related quality of life indicators (through the Functional Living Index Emesis scale)
- Collection of chemotherapy delays and/or dose reductions (Delay of chemotherapy administration due to CINV will be also evaluated as part of health economic endpoints, see below)

Health economic endpoints will be evaluated during the study cycles:

- Number of days and daily doses of rescue medication administered for the treatment of CINV
- Number of re-hydration bags given for at least grade 2 vomitings (CTCAE v5)
- The number of days of unplanned hospitalisations related to CINV and department of hospitalization (type of ward)
- The number of outpatient physician visits and health care consultations due to CINV (e.g., general practitioner)

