- The number of unplanned laboratory test including those at unplanned hospitalisations due to CINV
- Discontinuation of chemotherapy treatment due to CINV
- Delay of chemotherapy administration due to CINV
- Days of absence from work

CONFIDENTIAL

Confidential	MyRisk	Date: 05 February 2024
	Protocol	
	PROTOCOL NUMBER: IBA1160	Version: 5.1

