- Administer chemotherapy at a due time after antiemetic is given
- Safety findings (from diaries and inquiry)
- Rescue medications related to nausea and/or vomiting (from diaries and inquiry)
- Collect chemotherapy delay and/or dose reduction
- Collect and review the Patient's diary of cycle 1 and digitalize the data in the eCRF
- Collect and review the MAT of cycle 1 and digitalize the data in the eCRF
- Collect and review the FLIE questionnaire relevant to cycle 1
- Supply Patient's diary for cycle 2 and give instructions to the patient on how to fill it in from Day 1 to 5, and ask to bring it back on Day 1 of cycle 3
- Supply MAT for cycle 2, to be completed by the patient after 24 hours from chemotherapy administration and on Day 5 from chemotherapy administration, give instructions to the patient on how to fill it and ask to bring it back on Day 1 of cycle 3
- Supply FLIE for cycle 2, to be completed by the patient on Day 6 from chemotherapy administration (i.e., collection of data on nausea and vomiting from day 1 to day 5 from chemotherapy dosing), give instructions to the patient on how to fill it in and ask to bring it back on Day 1 of cycle 3
- Call patient between day 3 and 5 from chemotherapy to assess he/she is filling in the daily Patient's diary

CONFIDENTIAL

Confidential	MyRisk	Date: 05 February 2024
	Protocol	
	PROTOCOL NUMBER: IBA1160	Version: 5.1

### 3.6.3.4 VISIT 3: Day 1 of Cycle 3

- WOCBP will perform a urine dipstick pregnancy test, to exclude pregnancy
- Confirm eligibility of patients to chemotherapy according to the routine practice
- Check changes of the following screening visit parameters for the algorithm re-calculation:
  - o Expectation of nausea and/or vomiting YES/NO
  - o Chemotherapy regimen details
  - o Use of non-prescribed antiemetics at home in the prior cycle
  - o Nausea and/or vomiting in the prior cycle
  - o Number of cycles received
- Confirm the status of the added risk factors:
  - o Anticipatory nausea and/or vomiting in the prior cycle (YES/NO)
  - o Fatigue experience (symptom) YES/NO
  - o Duration of sleep during the night before chemotherapy
  - o Anxiety over the past 24 hours YES/NO
- Administered assigned antiemetic
- Administer chemotherapy at a due time after antiemetic is given
- Safety findings (from diaries and inquiry)
- Rescue medications related to nausea and/or vomiting (from diaries and inquiry)
- Collect chemotherapy delay and/or dose reduction

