### 8.4. Efficacy Analysis

All efficacy analyses will be performed on the FAS population. Also, analysis of the primary and secondary efficacy variables will be carried out on the Per Protocol population to assess the robustness of the findings. Safety outcomes will be analyzed on the Safety population.

CONFIDENTIAL

Confidential	MyRisk	Date: 05 February 2024
	Protocol	
	PROTOCOL NUMBER: IBA1160	Version: 5.1

The primary efficacy endpoint “Proportion of complete responses over three cycles of chemotherapy after the start of the MEC administration” will be analyzed by means of a generalized linear model (GLIM) with logit link function, binomial distribution, and with “study treatment” (NEPA + Dex or Standard of care), “carboplatin use” (yes or no) and “country” as factors. Moreover, the GLIM model will be parameterized with generalized estimating equations with an exchangeable working correlation matrix to take into account clustered data (i.e. three repeated measures corresponding to as many cycles of chemotherapy within each subject). Results will be reported as odds ratios with associated two-sided 95% confidence intervals and p-values.

The same statistical approach will be used for all the secondary efficacy endpoints except for the following outcomes “delay and/or dose reduction” which will be analyzed using a Stratified Wilcoxon Rank Sum test blocking for carboplatin use and country.

Missing data on the primary efficacy endpoint will be imputed using conventional Multiple Imputations approach. The SAS® MI procedure will be employed to perform multiple imputation in order to obtain Maximum Likelihood estimates which, by definition, are unbiased under a MCAR and MAR mechanism for missing values. Details on Multiple Imputations will be provided with the SAP.

Missing data on secondary efficacy endpoints will be imputed using last observation carried forward (LOCF). The overall type I family-wise error rate for testing the primary and the secondary efficacy parameters is controlled at the 0.05 significance level without the need for adjustments since the study is planned with a single primary endpoint and since secondary endpoints are only supportive of primary endpoint findings. All statistical analyses will be performed using SAS version 9.4 or later.

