9.4.1. Imputation of endpoints data

To achieve the largest possible sample, imputation techniques will be used to impute missing data for the FAS population. Missing data on the primary efficacy endpoint will be imputed using conventional Multiple Imputations approach. The SAS® MI procedure will be employed to perform multiple imputation in order to obtain Maximum Likelihood estimates which, by definition, are unbiased under a MCAR and MAR mechanism for missing values.

The following MI procedure code will be used to perform MI with 5 imputations.

```
PROC MI data = dataset seed=s out = MIdataset n impute = 5;
VAR study_treatment carboplatin country vis1_event - vis3_event;
CLASS study_treatment carboplatin country vis1_event - vis3_event;
monotone logistic;
RUN;
```

The exact names of the variables may differ.

9.4.2. Missing data within the FAS population on secondary efficacy endpoints will be imputed using the last observation carried forward (LOCF). Primary Efficacy Endpoint

The primary efficacy endpoint “Proportion of complete responses over three cycles of chemotherapy after the start of the MEC administration” will be analyzed by means of a generalized linear model (GLIM) with logit link function, binomial distribution and with “study treatment” (NEPA + Dex or Standard of care), “carboplatin use” (yes or no) and “country” as factors, using data from the overall period of three cycles.

Moreover, the GLIM model will be parameterized with generalized estimating equations with an exchangeable working correlation matrix to take into account clustered data (i.e. three repeated measures corresponding to as many cycles of chemotherapy within each subject). Results will be reported as odds ratios with associated two-sided 95% confidence intervals and p-values.

The results will be obtained via the GENMOD procedure, using following code:

```
PROC GENMOD data = dataset;
CLASS id study_treatment carboplatin country;
MODEL complete_response = study_treatment carboplatin country / dist = bin
link = logit;
REPEATED subject = id / type = exch covb corrw;
LSMEANS study_treatment / diff exp ilink cl;
RUN;
```

The exact names of the variables may differ.

With MI the code will be modified to:

```
PROC GENMOD data = dataset;
CLASS id study_treatment carboplatin country;
MODEL complete_response = study_treatment carboplatin country / dist = bin
link = logit;
REPEATED subject = id / type = exch ecovb;
LSMEANS study_treatment / diff exp ilink cl;

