9.4.3. Secondary Efficacy Endpoint

The same statistical approach as for the primary endpoint (GLIM) will be used for all the secondary efficacy endpoints with the exception of the following outcomes “delay and/or dose reduction” which will be analyzed using a Stratified Wilcoxon Rank Sum test blocking for carboplatin use and country, using following code (*delay_length* can be replaced with *amount_reduction*):

```

PROC NPAR1WAY data=dataset wilcoxon;
CLASS study_treatment;
VAR delay_length;
STRATA country carboplatin;
EXACT wilcoxon;
RUN;

```

The exact names of the variables may differ.

The code will be equivalent to the one used in the analysis of primary endpoint, only changing variable from *complete_response* to variables describing the secondary endpoints:

- Complete response during the acute (0-24h), delayed phase (25-120h), overall (0-120h) and daily in each cycle
- No emetic episode during the acute, delayed and overall phase and daily in each cycle
- Number of vomiting episodes during the acute, delayed and overall phase in each cycle
- No rescue medication during the acute, delayed and overall phase and daily in each cycle
- No significant nausea (maximum MAT scale = 2) during the acute, delayed and overall phase and daily in each cycle
- No nausea (MAT scale = 0) during the acute, delayed and overall phase and daily in each cycle
- Complete protection (no emetic episode, no rescue medication and no significant nausea) during the acute, delayed and overall phase and daily in each cycle
- Nausea and Vomiting-related quality of life indicators (through the Functional Living Index Emesis scale)

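### LOCF is not switched off for chemotherapy delay and dose reduction, so on per-cycle values a cycle never given takes a carried value and the test cannot register stopped chemotherapy

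*Protocol*

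**What the plan says.** Protocol 3.5 and SAP 6.2 list "Collection of chemotherapy delays and/or dose reductions" among the clinical secondary endpoints. Protocol 8.4 and SAP 9.4.3 treat it as a secondary efficacy outcome. They take it out of the GEE model and give it a test of its own, "which will be analyzed using a Stratified Wilcoxon Rank Sum test blocking for carboplatin use and country". The SAP code ranks one variable, "VAR delay_length", which can be replaced by the amount of reduction. The code has no cycle term and no category for stopped chemotherapy.

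The missing-data rule makes no exception for this endpoint. The protocol's sentence is "Missing data on secondary efficacy endpoints will be imputed using last observation carried forward (LOCF"; the SAP's, where 9.4.1 runs into 9.4.2, is "Missing data within the FAS population on secondary efficacy endpoints will be imputed using the last observation carried forward (LOCF".

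The visit schedule carries the item "Collect chemotherapy delay and/or dose reduction" at Visit 2 (3.6.3.3) and Visit 3 (3.6.3.4). It is not listed at Visit 1 or Visit 4.

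The plan foresees patients who do not go on to the next cycle: "Non-qualification to perform consecutive cycles (e.g., for toxicity" is a ground for exclusion in Protocol 3.4.5. "Discontinuation of chemotherapy treatment due to CINV" is a health economic endpoint and does not enter this test.

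**The concern.** A delay is defined only for a cycle that was given. When chemotherapy stops, there is no unrecorded delay to recover: the patient has lost the remaining planned doses. LOCF treats this as a gap and fills it with what happened one cycle earlier. A patient treated on time at cycle 2 who then stops would be ranked level with patients who received every cycle on time, and ahead of a patient who received cycle 3 late.

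At stake is the reading of one supportive endpoint. If the arms differ in how many patients stop chemotherapy, the delay and dose-reduction comparison would not show it, and its p-value would rest partly on values for cycles that never took place.

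**Working it through.** **1. Does the rule reach this endpoint?** Yes. The exception in Protocol 8.4 and SAP 9.4.3 concerns the test. The LOCF sentence covers secondary efficacy endpoints without exception, and neither document gives this endpoint another missing-data rule.

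**2. What the rule does, on per-cycle values.** Three illustrative patients:

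| Patient | Visit 2 value | Visit 3 value used |
|---|---|---|
| Cycle 2 on time, cycle 3 two weeks late | 0 days | 14 days (observed) |
| Cycle 2 on time, then stops | 0 days | 0 days (carried) |
| Stops after cycle 1 | none | none to carry |

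The second patient ranks better than the first. That the third leaves the test is an inference from the collection schedule; the plan gives no rule.

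**3. Does the unit of analysis matter?** Yes, and it is not stated. If the variable is a per-patient maximum, carrying cycle 2 forward changes nothing, because the carried value is already in the set. If it is a per-patient sum, a cycle-2 delay of d days becomes 2d. Neither reading has a category for a stop.

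**4. Does the Per Protocol analysis help?** No. Protocol 8.3 and SAP 8.1.3 require completion of the study, so patients who stop early are excluded.

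**5. How many patients?** The plan's own figures first. Missing proportions of 0%, 7.5% and 15% give 410 × 0.85 = 348.5 completers, which matches the stated 348. The sample size also reproduces. With d = {1, 0.925, 0.85} and correlation 0.5, the variance factor is (2.775 + 0.5 × 5.1225) / 2.775² = 0.693. The GEE log-odds formula for 71% versus 60% then gives 409, or 410 with equal arms. That calculation concerns complete response and does not depend on this point.

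If missingness is monotone:
- no Visit 2 or 3 value: 410 × 0.075 = 30.75, about 31
- cycle-2 value carried to cycle 3: 410 × (0.15 − 0.075) = 30.75, about 31
- together 61.5, about 62 of 410 (15%)

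This is an upper guide, because the rates are for missing complete response from any cause and not for chemotherapy stops.

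**6. Effect on the test (illustration).** The stop and delay rates below are assumptions; the documents give none. There are 205 patients per arm, half of the stops fall before cycle 2, and the test is an unstratified two-sided Wilcoxon test at 5% on the cycle-3 value. In the first five rows the delay risk is the same in both arms.

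| Stops, NEPA vs control | Delay risk | LOCF rejects | Stop = worst rank rejects |
|---|---|---|---|
| 15% vs 15% | 10–30% | about 5% | about 5% |
| 5% vs 10% | 15% | about 5% | about 21% |
| 12% vs 18% | 15% | about 5–6% | about 26–27% |
| 10% vs 20% | 10–30% | about 5% | about 50–65% |
| 7.5% vs 22.5% | 10–30% | about 5% | about 85–95% |
| 15% in both arms | 10% in one arm, 20% in the other | about 77–79% | about 36–40% |

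Arithmetic check for stops of 10% vs 20% with 20% delayed. Under LOCF the share with any delay is 20% in both arms, whatever the stop rate. With a stop counted as worst it is 0.10 + 0.90 × 0.20 = 28% against 0.20 + 0.80 × 0.20 = 36%. Carrying a zero from cycle 1 instead of dropping early stoppers leaves the LOCF rate at about 5%.

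**The case against.** **Stops are reported elsewhere.** A reader might infer that stopped chemotherapy is hidden from the report. It is not. Discontinuation of chemotherapy due to CINV has its own table on the Full Analysis Set (14.4-6). The adverse event summary in SAP 9.5.1 counts discontinuations due to adverse events. Discontinued subjects are listed (16.2.1-1). SAP 9.1 presents tables by treatment group. This stands, with a limit: none of these outputs enters the delay and dose-reduction test, and Table 14.4-6 covers only stops attributed to CINV.

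**LOCF need not reverse the result.** A reader might infer that the arm with more stops would look better. None of the calculations shows that. With delays set equal in both arms, a 5% rejection rate is the correct behaviour of a test of delay. The worst-rank test rejects more often because it answers a wider question. What stands is that the LOCF test is insensitive to stopping.

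**Carried values are not known to be mostly zero.** The documents give no figure for delays or reductions, so they do not support saying that the carried value is usually no delay and no reduction.

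**Worst rank has a price.** Making it the main test would create a composite that no stated objective asks for. When delays differ and stops do not, its power is about half that of LOCF (last row of the table). When only stops differ, 10% vs 20%, a direct comparison of stop proportions rejects in about 82% of trials, against about 62% for worst rank under the same delay assumptions. Sorting stops by cause is also fragile in an open-label trial where patients may withdraw without giving a reason. This stands and shapes the fix.

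**The endpoint is supportive.** Protocol 8.4 says so of all secondary endpoints. This limits the weight of the point but does not make the carried values meaningful.

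**Conclusion.** The point holds in a limited form. As written, LOCF applies to chemotherapy delay and dose reduction. If the test uses per-cycle values, it assigns a value to a cycle that was never given, or has nothing to assign after a stop in cycle 1. In either case the Wilcoxon test cannot register stopped chemotherapy, and the Per Protocol repeat does not cure this.

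The size is at most about 31 patients with carried values and about 31 with none, if missingness is monotone and every loss is a chemotherapy stop. The contrast between arms is distorted only if stopping differs by arm. With equal stopping the test keeps its 5% level in the simulations, and the change in planned dosing is understated in both arms. The primary endpoint, its multiple imputation and the sample size of 410 are not affected.

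**What to change.** In Protocol 8.4 and SAP 9.4.1 and 9.4.3:

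- Exempt chemotherapy delay and dose reduction from LOCF. State that a cycle not given because chemotherapy stopped is an outcome and not missing data.
- State whether the test variable is per cycle or per patient and, if per patient, how it is formed.
- Keep the stratified Wilcoxon test on observed delays and reductions as the main test.
- In Tables 14.2-10 and 14.2-11, show the number of patients who stopped chemotherapy, by arm and recorded reason.
- Add a stratified Wilcoxon test with a stop ranked worst as a sensitivity analysis. Count all chemotherapy stops, so that it does not depend on open-label attribution of the reason. Ranks suffice, so no numeric delay has to be invented.

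The cost is a few sentences of text, one derived variable, one extra analysis and slightly fewer values in the main test. Before database lock, check that the eCRF separates stopping chemotherapy from leaving the study. The documents make this explicit only for stops due to CINV.

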9.4. Analysis of Efficacy

All efficacy analyses will be performed on the FAS population. Also, analysis of the primary and secondary efficacy variables will be carried out on the Per Protocol population to assess the robustness of the findings.

The overall type I family-wise error rate for testing the primary and the secondary efficacy parameters is controlled at the 0.05 significance level without the need to adjustments since the study is planned with a single primary endpoint and since secondary endpoints are only supportive of primary endpoint findings. All statistical analyses will be performed using SAS version 9.4 or later.

Information on nausea and vomiting during the acute and delayed phase and overall from MAT will be considered for analysis. For analysis of daily occurrences, MAT information will be used for Day 1 (identical to acute phase), otherwise data from Patient's Diary will be used.

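### The plan claims family-wise error control at 0.05 over primary and secondary endpoints, but only the primary test has it

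*Protocol*

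**What the plan says.** Protocol 8.4 (Efficacy Analysis) says: "The overall type I family-wise error rate for testing the primary and the secondary efficacy parameters is controlled at the 0.05 significance level". It adds that no adjustment is needed, "since the study is planned with a single primary endpoint and since secondary endpoints are only supportive of primary endpoint findings". SAP 9.4 carries the same statement with the same two reasons.

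The secondaries are formally tested. Protocol 8.4: "The same statistical approach will be used for all the secondary efficacy endpoints except for the following outcomes" delay and dose reduction, which get a stratified Wilcoxon test. For the shared approach, "Results will be reported as odds ratios with associated two-sided 95% confidence intervals and p-values". SAP 9.4.3 confirms this: "The code will be equivalent to the one used in the analysis of primary endpoint, only changing variable" to each secondary in turn.

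Most lines in that list expand into several tests, for example "No emetic episode during the acute, delayed and overall phase and daily in each cycle". Neither document orders the secondaries, makes their testing depend on the primary result, splits alpha or adjusts p-values.

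**The concern.** The sentence names a family (primary and secondary efficacy parameters) and claims a property for it. Neither reason given delivers that property. Having one primary endpoint means the primary test needs no correction; it does nothing for the other tests. Calling the secondaries supportive is a good reason to draw no confirmatory conclusion from them, but it is not a procedure that limits false positives among them.

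The primary inference is not at stake. What is at stake is how secondary results may be described. A study report could cite this sentence to present p < 0.05 for nausea, complete protection, one phase or one day as error-controlled. The trial is open label and these outcomes are patient-reported, so their strength should not be overstated. Because both governing documents say the same thing, neither corrects the other.

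**Working it through.** **1. The plan's 0.05.** For the primary test alone the rate is 1 − 0.95 = 0.05, as stated. The sample size is built on that one test. Inputs from Protocol 8.2: 71% vs 60%, three cycles, missing 0%, 7.5% and 15%, correlation 0.5.

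- Variance factor, with observed proportions d = 1, 0.925, 0.85: f = [Σd + 0.5·Σ(i≠j) d_i·d_j] / (Σd)² = (2.775 + 0.5 × 5.1225) / 2.775² = 0.693.
- Log odds ratio = ln(0.71/0.29) − ln(0.60/0.40) = 0.490.
- n per arm = (1.960 + 0.842)² × 0.693 × [1/(0.71 × 0.29) + 1/(0.60 × 0.40)] / 0.490² ≈ 204.5, or 409 in total. Power at 205 per arm is 80.1%.

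The stated 410 and 80% reproduce, and they belong to the primary test only.

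**2. Number of tests, cycles pooled as in the SAP code.**

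- Six yes/no endpoints: complete response, no emesis, no rescue, no significant nausea, no nausea, complete protection.
- Seven windows: acute (SAP 9.4 treats Day 1 as the same), delayed, overall, and Days 2 to 5.
- 6 × 7 = 42, less 1 because pooled overall complete response is the primary: 41.
- Plus 3 vomiting counts, 1 FLIE total, and 2 tests for delay and dose reduction: 47 secondaries. With the primary, 48.
- The two FLIE domains (SAP 7.9) add 2. Daily vomiting counts for Days 2 to 5 add 4: Protocol 3.5 and SAP Figure 14.2-4 include them, SAP 9.4.3 does not.
- The family is therefore 48 to 54 tests. Per Protocol repeats are not counted.

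The endpoints are worded per cycle. Tested that way, the secondaries number 42 × 3 + 3 × 3 + 3 + 2 = 140, or 146 with the FLIE domains. Daily vomiting counts add 12 (152 or 158).

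**3. Family-wise rate, all null hypotheses true, each test two-sided at 0.05.** Under independence it is 1 − 0.95^k. With common correlation ρ it is 1 − ∫ φ(u)·[Φ((1.96 − √ρ·u)/√(1−ρ)) − Φ((−1.96 − √ρ·u)/√(1−ρ))]^k du.

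| Tests k | ρ = 0 | 0.5 | 0.7 | 0.9 | 0.95 |
|---|---|---|---|---|---|
| 1 | 0.05 | 0.05 | 0.05 | 0.05 | 0.05 |
| 2 | 0.098 | 0.091 | 0.083 | 0.070 | 0.065 |
| 10 (primary + one per listed secondary) | 0.40 | 0.29 | 0.21 | 0.13 | 0.10 |
| 48 | 0.91 | 0.61 | 0.40 | 0.19 | 0.14 |
| 54 | 0.94 | 0.64 | 0.41 | 0.20 | 0.14 |
| 140 | 0.999 | 0.84 | 0.55 | 0.24 | 0.16 |

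The number of tests matters less than the correlation, and no row beyond the first reaches 0.05.

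**4. Illustration with nested endpoints.** The secondaries overlap heavily, so 4,000 null trials per scenario were simulated. Each had 205 patients per arm, three complete cycles and 47 tests; daily emesis, rescue and nausea came from an assumed latent normal model. Assumed rates were 60% overall complete response, 40% significant nausea and 60% any nausea. Patient means over cycles were compared by z test, and the two delay and dose tests were taken as independent. With a between-cycle correlation of complete response of 0.49 (the protocol assumes 0.5) the family-wise rate was 0.39. It ranged from 0.47 to 0.28 as that correlation went from 0.45 to 0.72. The primary test stayed at 0.045 to 0.054.

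**The case against.** The strongest reply is that the sentence largely corrects itself. Its reasons describe one confirmatory test, with secondaries that only back it up. Leaving such secondaries unadjusted is accepted practice, and no passage plans a confirmatory secondary claim. On that reading the secondaries count only after a significant primary, and if all nulls are true the chance of any false claim is then at most 0.05. The table above would not describe that use.

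Much of this stands: no adjustment is needed, and the fault is one of statement, not of analysis. But the gate is written nowhere, and it would not secure the claim. Suppose the primary effect is real, with 80% power, and the secondaries are null. For 9 independent secondaries the chance of a false secondary finding is 0.80 × (1 − 0.95⁹) = 0.80 × 0.37 = 0.30. For 48, with the primary in the same common-factor model, it is about 0.47, 0.27 and 0.10 at correlations 0.5, 0.7 and 0.9. It falls to about 0.05 only with few, nearly identical tests (9 at correlation 0.95).

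It is also fair that the simulation illustrates its assumptions more than this trial. It uses neither the planned GEE with carboplatin and country, nor the expected missing data, nor LOCF. The conclusion does not rest on it.

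**Conclusion.** The statement is wrong as written for the secondary endpoints. The 0.05 level holds for the primary test and for nothing else. For the family named in the sentence, the global-null rate runs from about 0.14 to above 0.9 for 48 to 54 tests, depending on correlation.

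Three things here are assumptions: the correlation between endpoints, the test count (read from the endpoint lists), and a 0.05 threshold for each secondary, since the documents set none. The direction depends on none of the exact values: unadjusted tests in a family exceed 0.05 unless they are perfectly correlated. The consequence is limited to how secondary results may be described.

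**What to change.** Replace the sentence in Protocol 8.4 and SAP 9.4 with:

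> The two-sided 0.05 level applies to the single primary test. Secondary p-values and confidence intervals are nominal, not adjusted for multiplicity, and support no confirmatory claim.

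The cost is one sentence in each document. Endpoints, models, sample size and power stay as they are. The sponsor gives up an error-control statement that the design does not have. A multiplicity procedure would be needed only if the sponsor wanted confirmatory secondary claims, which neither document plans.
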